15.4 Analysis of Secondary Endpoints

The statistical analyses of the secondary endpoints will follow the same regression model approach as with the primary endpoint using a regression model appropriate for the outcome type. For example, we will use linear regression to analyze continuous endpoints such as MaxPC and polytomous logistic regression for categorical endpoints of decision support intervention (DSI) coaching versus usual care.

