10.2 Contact 2.1 Obtaining Informed Consent

Includes: enrolling them; administering all baseline/pre-intervention surveys (e.g. SF-12, EPIC, demographics, brief lifestyle questions (e.g., smoking, physical activity), as well as choice predisposition (CP), decision self-efficacy (DSE) and control preferences scale (CPS)) [30, 32, 34, 35]. Site study coordinator alerts patient they must allow time before and after their visit to fill out surveys (on arrival and before leaving the clinic). Note this contact could conceivably be by telephone and the surveys could be filled out by Internet. After all surveys are complete, the site staff will enter the patient into the UCSF system to trigger a call from a student coach.

1. After obtaining the informed consent in REDCaP the CRC will complete the following forms in REDCaP:
 - a. **Subject Identifier Form** in REDCaP and Registration Form in CaPSURE. This action assigns the subject a unique research ID and assignment to study arm (usual care vs, intervention) in REDCaP and CaPSURE secure websites.
 - b. Complete **Study Eligibility Form**.
 - c. Complete **Study Biopsy Form**. Record medical history, including: PSA at diagnosis; tumor stage; prostate volume; biopsy diagnosis date with primary and secondary Gleason grade; and ECOG performance score [36].
2. REDCaP will provide participant with the access to patient reported-surveys and demographics data.
3. If the participant opts for the paper-mode, the CRC will provide the participant with a paper packet of patient surveys.

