15 STATISTICAL METHODS AND CONSIDERATIONS

Prior to the analysis of the final study data, a Statistical Analysis Plan (SAP) will be written describing all analyses that will be performed. The SAP will contain any modifications to the analysis plan described below.

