15.3 Analysis of Primary Endpoint

The primary statistical analysis will compare the probability of correctly responding to the two knowledge survey questions between subjects randomized to the intervention and control sites using logistic regression. The primary predictor of the logistic model will be the binary, site-specific intervention indicator. We will also include site, time and intervention group by time interaction terms. Since randomization by site may not balance, all relevant sociodemographic and clinical characteristics of the subjects may be included in the models; we will also include other factors that are not balanced between the groups. We will assess balance by comparing means of continuous characteristics using two sample t-tests and by comparing categorical characteristics using chi-square tests.

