15.6 Sample Size and Randomization

We will base sample size calculations on the comparison of the probability of correctly responding to the two survey questions between subjects at the intervention versus control sites with a design effect correction to accommodate the potential correlation of responses within sites [44]. That is, we will inflate the sample sizes resulting from standard sample calculations for the comparison of two proportions by the design effect, $1 + (n-1)*\rho$, where n is the sample size per site and ρ is the intraclass correlation coefficient of the primary binary response[45]. We are interested in detecting an alternative where the probability of the primary response increases from 0.5 in the control sites to 0.75 in the intervention sites. Standard power calculations for chi-square tests to compare two proportions [45] show that tests based on a total sample size of 116 would have power 0.8 to detect the alternative of interest. Since our study design involves 8 clusters (four sites measured in two time periods), our initial design would include 15 subjects measured in each site at each time. Preliminary data indicate that the intraclass correlation coefficient of the primary response is quite low within sites; the estimated intraclass correlation coefficient was less than 0.01. This estimate produces a design effect of 1.14 and we inflate the required number of subjects per site and time to 17 for a total sample size of 136.

Randomization: At baseline, this study will randomize two sites to the intervention and two sites to serve as controls. There are six possible assignments of two intervention and control sites in our study and we will generate a uniform (0,1) random number to select one of them.

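### Section 15.4 does not fix baseline (T1) decision self-efficacy as a covariate in the analysis of pre-visit (T3) decision self-efficacy, although both arms provide it

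*Combined protocol and SAP*

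**What the plan says.** - **Endpoint and timing.** Section 5.2 makes DSE a secondary endpoint. Table 2 schedules it at T1 (consent) and T3 (pre-visit), without a split by arm. Table 1 lists T1 and T3 surveys in both arm columns.
- **Baseline collection.** Section 10.2, which is not restricted to the intervention arm, lists among the pre-intervention surveys "as well as choice predisposition (CP), decision self-efficacy (DSE) and control preferences scale (CPS". Section 10.5 collects DSE again on arrival at the clinic; it calls that survey Time 2 where the tables say T3.
- **Secondary model.** Section 15.4: "The statistical analyses of the secondary endpoints will follow the same regression model approach as with the primary endpoint".
- **Terms inherited from 15.3.** Besides the intervention indicator: "We will also include site, time and intervention group by time interaction terms". Further covariates have two routes. One is discretionary: "all relevant sociodemographic and clinical characteristics of the subjects may be included in the models". The other depends on the data: "we will also include other factors that are not balanced between the groups", with the rule "We will assess balance by comparing means of continuous characteristics using two sample t-tests" (chi-square for categorical characteristics). No significance level is given.
- **Elsewhere.** Section 15.2 does not name DSE among its examples of baseline characteristics. Section 5.4 lists DSE among covariates for exploratory analyses. Section 15 leaves room for change: "The SAP will contain any modifications to the analysis plan described below".
- **Usual care.** Section 5.2 mentions DSE in that arm only as measured before the appointment. It does not mention the two occasions that Table 2 schedules.

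**The concern.** The baseline value of an outcome is usually among its strongest predictors. Putting it in the model reduces the variance of the treatment effect even when the arms are perfectly balanced at baseline. Including it only when a test finds imbalance therefore ties the decision to the wrong criterion. The discretionary route has a different fault: it leaves the DSE model undecided until the data can be seen.

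What is at stake is mainly precision. Bias protection is secondary. Every site contributes men to both arms and site is in the model, so stable site differences cancel. T1 DSE could become unbalanced only through shifts between periods within a site, or through selective recruitment by clinic staff, who are not blinded (8.2). The documents give no evidence of either.

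**Working it through.** **Inputs.** Section 15.6 compares 0.50 with 0.75 at power 0.8. The usual pooled formula, two-sided 5% (level assumed; the plan states none), reproduces its total:

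(1.960·√(2·0.625·0.375) + 0.842·√(0.25 + 0.1875))² / 0.25² = 57.7, so 58 per arm and 116 in all.

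The design effect is 1 + 14·0.01 = 1.14, and 15·1.14 = 17.1. The plan then states "we inflate the required number of subjects per site and time to 17 for a total sample size of 136". That gives 136/2 = 68 per arm. These figures serve the primary endpoint; the documents give no power for DSE. The T1–T3 correlation r is not given either, so r = 0.3, 0.5 and 0.7 are assumed.

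**Gain from fixed adjustment.** Residual variance is multiplied by 1 − r². Detectable difference, two-sided 5%, 80% power, no design effect: 2.80·√(2/68) = 0.480 SD, times √(1 − r²).

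| r | Fall in variance | Detectable, 68 per arm | Detectable, 80 per arm |
|---|---|---|---|
| none | – | 0.480 SD | 0.443 SD |
| 0.3 | 9% | 0.458 SD | 0.423 SD |
| 0.5 | 25% | 0.416 SD | 0.384 SD |
| 0.7 | 49% | 0.343 SD | 0.316 SD |

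With the plan's design effect of 1.14 and 68 per arm, 0.51 SD falls to 0.49, 0.44 and 0.37 SD.

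**What the balance rule keeps.** Simulation with 4 sites × 2 periods × 17 men, model site + period + intervention, 6,000 trials per setting, balance t-test at an assumed 5%, discretionary route not used. With no true imbalance, the variance of the effect relative to no adjustment was:

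| r | T1 DSE always in | T1 DSE in only if flagged | Share of gain kept |
|---|---|---|---|
| 0.3 | 0.916 | 0.975 | 0.025/0.084 = 30% |
| 0.5 | 0.766 | 0.936 | 0.064/0.234 = 27% |
| 0.7 | 0.502 | 0.858 | 0.142/0.498 = 29% |

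**Bias if T1 DSE were truly unbalanced.** At true imbalances of 0.1, 0.2, 0.3 and 0.4 SD the test flags 9%, 21%, 41% and 64% of trials. At 0.3 SD, for r = 0.3, 0.5 and 0.7:

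- no adjustment: 0.088, 0.150, 0.209 SD;
- balance rule: 0.032, 0.056, 0.074 SD on average;
- fixed adjustment: 0.00.

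Over 0.1 to 0.4 SD, the average bias under the rule never exceeds 0.075 SD. The worst case is an observed imbalance just below the flag threshold of 1.978·√(2/68) = 0.339 SD. Left unadjusted, it shifts the estimate by r times that: 0.102, 0.170 and 0.237 SD.

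**The interaction term does not stand in for the baseline score.** Section 15.6 uses time for the two trial periods. On that reading, with 0/1 coding, intervention × period = 0.5·period + 0.5·intervention − 0.5·(indicator of the sites that start with the intervention). The last term is a sum of site indicators. Site + period + intervention has 6 columns and rank 6; adding the interaction gives 7 columns and still rank 6. Adding T1 DSE instead gives 7 columns and rank 7, so the proposed model can be fitted.

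**The case against.** **Time might mean survey occasion.** T1 and T3 would then both be outcomes and the interaction would carry the change from baseline, a reading that the pre/post language in 5.2 encourages. But 15.6 uses time for period, and 15.4 borrows a model written for a primary outcome assessed at one occasion, just before the visit. The reading is strained, and a change-type analysis would recover less precision than covariate adjustment. The ambiguity does need resolving.

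**The size rests on assumptions.** The correlation, the test level and the balance threshold are all assumed, and at r = 0.3 the gain is small. Table 2 lists DSE as a single item. If it is analysed as categorical, the linear-model figures do not carry over directly, and covariate adjustment changes the odds ratio being estimated. This stands: the figures are illustrative.

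**The balance-rule comparison leaves out the discretionary route.** True. Analysts could choose to include T1 DSE and obtain the full gain, but that choice would not have been prespecified.

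**The SAP can settle it.** It can. It is still to be written, and the current text sets a weaker rule for it to inherit.

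**Section 5.2 does not contradict Table 2.** T1 and T3 both precede the appointment, so its sentence on usual care is incomplete rather than incompatible. That is fair; it still needs aligning.

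**It is one secondary endpoint.** Also true, and it limits the importance of the point.

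**Conclusion.** The concern holds. The trial schedules a pre-intervention DSE score in both arms, yet the plan does not commit to using it in the analysis of T3 DSE. The covariate rule it sets keeps about 27% to 30% of the available precision gain when there is no true imbalance and only the balance test operates. The gain ranges from minor at r = 0.3 to about half the residual variance at r = 0.7, under a linear model and an assumed two-sided 5% level. The omission itself is certain from the text; its size is not, because r is unknown. Any bias is hypothetical. This should be changed, but it threatens neither the primary analysis nor the validity of an unadjusted DSE comparison.

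**What to change.** In 15.4 or the SAP:

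- Prespecify T1 DSE as a covariate for T3 DSE whatever the balance tests show, alongside intervention, site and period, and base the DSE conclusion on the adjusted between-arm difference.
- Do not take this estimate from the intervention-by-time term. State whether time means trial period or survey occasion.
- Give a simple rule for a missing T1 item, for example the T1 mean pooled over arms. Section 12.4 mentions imputation only for examining sensitivity to missing data.

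In 5.2, state that usual-care participants complete DSE at T1 as well as T3, in line with Table 2.

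The cost is wording only. The T1 and T3 data are already scheduled in both arms, so no visit, survey item or increase in sample size is needed.

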6.2 Inclusion Criteria

1. Male \geq 18 years of age and newly diagnosed PCa (within 3-months).
2. Documentation of a low-risk PCa diagnosis as evidenced by clinical features of the following criteria:
 - a. PSA test at diagnosis \leq 15 ng/ml
 - b. Localized PCa (cT1/T2,N0,M0)
 - c. Biopsy Gleason grade 2-6 OR (or 3+4 AND \leq 33% cores are positive for adenocarcinoma)
 - i. A minimum of 10 diagnostic cores taken by a systematic directed approach. Sampling may be obtained by target TRUS or MRI imaging.
 - d. No treatment yet
 - i. No previous radiation or simultaneous use of androgen deprivation
 - ii. Prior use of 5-alpha reductase inhibitor is allowed if they have been stopped for 6 or more months and biopsy performed when patient was not taking the drug
 - e. English language proficient and ability to provide ICF
 - f. Managing urologist considers them a candidate for active surveillance
3. Written informed consent (and assent when applicable) obtained from subject and ability for subject to comply with the requirements of the study, including the ability to read and speak English.

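### The management-choice model in section 15.4 does not prespecify T1 choice predisposition, carries an intervention-by-period term that cannot be estimated with fixed sites, and has no rule for sparse categories

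*Combined protocol and SAP*

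**What the plan says.** Choice of management is a secondary objective and endpoint in the synopsis and in section 3.2. Section 1.1 names the options as active surveillance, surgery and radiation.

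Section 15.4 has the secondary endpoints follow the primary regression approach, with a model suited to the outcome type. Its illustration for categorical outcomes is "polytomous logistic regression for categorical endpoints of decision support intervention (DSI) coaching versus usual care". It does not name management choice, but that is the secondary endpoint that is clearly categorical.

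The terms carried over come from section 15.3: an intervention indicator, then "We will also include site, time and intervention group by time interaction terms". Sociodemographic and clinical characteristics are optional there. Factors found unbalanced by t-tests or chi-square tests are added.

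Section 10.2 lists among the baseline surveys "as well as choice predisposition (CP), decision self-efficacy (DSE) and control preferences scale (CPS"). Table 2 marks choice predisposition at T1, T3 and T4. Under section 8.4, the coaching team contacts the patient only after the baseline surveys are complete, so the T1 value precedes the intervention. Section 5.4 lists it only among covariates for exploratory analyses.

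Section 6.2 requires of every man: "Managing urologist considers them a candidate for active surveillance". No section gives an expected management split, a rule for combining categories, or a power figure for this endpoint.

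**The concern.** Management choice is the secondary endpoint that speaks to over-treatment, the problem that sections 1.1 and 2 put first. Three matters weaken its analysis.

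- A man's leaning before the intervention is a natural predictor of what he finally chooses. It is already collected in both arms, yet under 15.3 it is sure to enter the model only if a balance test happens to flag it.
- The interaction term duplicates information already in the model. Software will either fail or drop a column, and what the intervention coefficient means then depends on which column goes.
- All men are surveillance candidates, so surgery or radiation may be rare. The plan does not say what happens to a three-category model in that case.

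**Working it through.** **The plan's own sample size.** Section 15.6 takes a response that "increases from 0.5 in the control sites to 0.75 in the intervention sites" and power 0.8. Alpha is not stated; 0.05 two-sided is assumed.

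- Per arm: [1.96·√(2·0.625·0.375) + 0.842·√(0.5·0.5 + 0.75·0.25)]² / 0.25² = 57.7, so 58, and 116 in total. This matches the plan.
- 116/8 = 14.5, so 15 per site and period. Design effect 1 + 14·0.01 = 1.14; 15·1.14 = 17.1, taken as 17; 17·8 = 136.

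The figure reproduces, but it is for the binary knowledge endpoint only. Management choice is recorded separately from the knowledge survey, so up to 160 − 12 = 148 men might have it.

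**Size of the model.** Intercept, intervention, three site dummies, time and intervention-by-time make 7 columns. Three categories need 2 logits, so 7·2 = 14 nominal coefficients before covariates.

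**The interaction.** Let x be intervention (0/1), t period (0/1), and s = 1 for sites that start in usual care. Here s is a sum of site dummies. The crossover fixes x = 1 − s in period 1 and x = s in period 2. Then x·t = (x + s + t − 1)/2 in all four cases:

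| s | t | x | (x + s + t − 1)/2 | x·t |
|---|---|---|---|---|
| 0 | 0 | 1 | 0 | 0 |
| 0 | 1 | 0 | 0 | 0 |
| 1 | 0 | 0 | 0 | 0 |
| 1 | 1 | 1 | 1 | 1 |

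So the matrix has rank 6 of 7, and 6·2 = 12 coefficients are estimable. Take site 1 as reference and sites 3 and 4 as starting in usual care. If software keeps x·t and drops the site 4 dummy (coefficient γ), then because s = 2x·t − x − t + 1, the printed intervention coefficient becomes β − γ and the printed interaction 2γ. A site difference is then mixed into the reported effect.

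**Sparse categories.** With 34 men per site and a share q in the rarest category (assumed), P(some site has none) = 1 − (1 − (1 − q)^34)^4:

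| q | 6% | 8% | 10% | 12% | 15% | 20% |
|---|---|---|---|---|---|---|
| P | 41% | 21% | 11% | 5% | 1.6% | 0.2% |

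With 148 men (37 per site) it is 17% at 8% and 8% at 10%. The same formula applied to surveillance versus any treatment gives 0.2% if 20% are treated and 1.6% if 15% are.

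**Choice predisposition.** Simulated power, 136 men, 1,000 runs per row, interaction omitted, predisposition split at its median. Surveillance shares are usual care versus intervention; r is the assumed latent correlation between T1 predisposition and final choice.

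| Shares | r | Three-category, 2 df | Binary | Binary + T1 CP | Gain from CP (points) |
|---|---|---|---|---|---|
| 50 vs 70% | 0.5 | 0.575 | 0.685 | 0.736 | 5.1 |
| 60 vs 80% | 0.5 | 0.656 | 0.739 | 0.787 | 4.8 |
| 70 vs 85% | 0.5 | 0.512 | 0.596 | 0.634 | 3.8 |
| 80 vs 90% | 0.5 | 0.343 | 0.361 | 0.378 | 1.7 |
| 50 vs 70% | 0.7 | 0.590 | 0.685 | 0.795 | 11.0 |
| 60 vs 80% | 0.7 | 0.650 | 0.730 | 0.813 | 8.3 |
| 70 vs 85% | 0.7 | 0.479 | 0.556 | 0.616 | 6.0 |
| 80 vs 90% | 0.7 | 0.389 | 0.393 | 0.435 | 4.2 |

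A separate simulation of the binary model gave gains of about 3 to 10 points, with type I error near 5%. Every row keeps the surgery-to-radiation ratio equal in the two arms, which favours the binary contrast over the 2-df test. The comparison of those two columns should be read with that in mind.

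**The case against.** A reader might infer that about 136 men cannot support the polytomous model at all. The documents do not support that.

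- **The split is unknown.** Being a surveillance candidate is not the same as choosing surveillance, and sections 1.1 and 2 describe active treatment as frequent. At an assumed 50/30/20 split the model without the interaction can usually be fitted: some coefficient diverged in only 3 to 4% of runs (50 vs 70% surveillance), against 76% at 80 vs 90%.
- **An empty site is not an empty comparison.** Only that site's coefficient diverges; the intervention effect is still estimated from the other sites. In simulations with equal shares in both arms, the intervention coefficient itself diverged in 0% of runs at 50/30/20, 2% at 60/25/15, 12% at 70/20/10 and 27% at 80/12/8.
- **The three-category model does give one answer**, a 2-df test. The decision aid sets out the harms of surgery and radiation separately, so a shift between them is a plausible effect that a binary outcome would hide.
- **Section 15.4 is illustrative.** Section 15 says that a SAP is still to be written and may modify the analyses.

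All four stand, and they rule out replacing the polytomous model outright. They leave untouched the aliased term, the covariate that is not prespecified and the missing sparse-category rule. That a SAP is still to come is a reason to settle these points in it.

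**Conclusion.** The point holds in this limited form.

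- **Interaction:** certain, given fixed site effects and a two-level period. It is not a sample-size problem, so more men would not cure it. It would not be exact with continuous calendar time or random site effects. The plan specifies neither, and sections 4.1 and 15.6 describe two periods. The same algebra applies to any model that carries the 15.3 terms.
- **T1 choice predisposition:** it would be wrong to say that the plan ignores it, since 5.4 gives it an exploratory role and 15.3 could admit it. What is missing is prespecification. The gain of roughly 3 to 10 points (1.7 to 11.0 in the table) rests on an assumed correlation for which the documents give no figure.
- **Sparsity:** a conditional risk. It matters if the rarest option is near or below 10% and is minor from about 15% upward.

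**What to change.** In section 15.4, or in the SAP that section 15 promises:

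1. Name management choice as an endpoint of this model. Prespecify T1 choice predisposition as a covariate whatever the balance tests show, and state its coding. The T3 and T4 values follow the intervention and must not be used as covariates.
2. Use intervention, site and period as the design terms, and drop intervention-by-period when site is fixed.
3. Prespecify surveillance versus any active treatment, by binary logistic regression, as a contrast that is always reported. It answers the over-treatment question in the rationale.
4. Keep the three-category comparison as a 2-df test where it can be fitted. State the sparse-data rule in advance, for instance no man in a category at some site, or estimates that are not finite. The binary contrast is then the fallback, with surgery and radiation shown as counts and percentages by arm.

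The cost is wording; no new data are needed. The downsides are that the odds ratio becomes conditional on predisposition, that men without a T1 value need a stated rule applied alike in both arms, and that under the fallback surgery versus radiation is descriptive only.

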15.5 Interim Analysis

Not Applicable

